6.2.1.1.4. Missing Data: Adverse Event Date Imputation

Follow the general rules outlines in [Section 6.2.1.1](#).

6.2.1.2. Subgroup Analysis

No subgroup analyses are planned due to the expected small sample size.

6.2.1.3. Multicenter Studies

This is a multicenter study; however, the expected sample size is not sufficient to perform any meaningful efficacy summaries by center.

6.2.1.4. Hypothesis Testing and Significance Level

No statistical hypothesis testing will be performed. Efficacy data will be analyzed using descriptive statistics.

6.2.1.5. Sensitivity Analyses

No sensitivity analyses will be performed.

6.2.2. Secondary Analyses**6.2.2.1. Neurologic Examination**

A summary of the frequency and percentage of subjects with neurologic examination findings [REDACTED] will be presented by visit.

6.2.2.2. Developmental Assessments

Changes from baseline to post-treatment assessments in the Bayley-III will be summarized using descriptive statistics. The raw, scaled, age-equivalent, and DQ scores will be summarized for the Cognitive Scale and Fine Motor and Gross Motor subtests. Additionally, the composite score for cognitive and motor scales will be summarized for subjects up to 42 months in age or subjects with severe disability and the Bayley assessment is more appropriate. Language Scale results will be displayed in a by-subject data listing.

A summary of the frequency and percentage of subjects at each level of the 5-level classification system of the GMFCS-E&R will be presented by visit.

Changes from baseline to post-treatment assessments in the WPPSI will be summarized using descriptive statistics. A by-subject data listing of all WPPSI IV assessments will be produced.

6.2.2.3. Seizures

The number and frequency of subjects with seizures prior to treatment with ORGN001 and over each 6-month period on study will be summarized. In addition, the number of subjects with medication changes due to seizures will be summarized. A by-subject data listing of seizure data and changes in medications since the last visit, along with reasons for the change will be produced.

Seizures collected as AEs will be summarized as AEs.

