**Efficacy variables:**

Changes in urine and blood SSC levels (urine levels normalized to urinary creatinine), clinical findings from neurologic examination, motor and cognitive assessment results (Bayley-III, GMFCS -expanded and revised, WPPSI), incidence of seizures (if present), findings from neuroimaging (magnetic resonance imaging scan), growth parameters (body weight, body length, head circumference), changes in feeding patterns

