### 12.5.1 Definition of an Adverse Event

An AE is defined as any unfavorable and unintended sign (eg, including an abnormal laboratory finding), symptom or disease temporally associated with the use of a medicinal product or procedure, whether or not considered related to the medicinal product or procedure that occurs during the course of the clinical study.

Exacerbations of a chronic or intermittent pre-existing condition including either an increase in frequency and/or intensity of the condition are all to be considered AEs.

Abnormal test findings may be considered AEs. If an abnormal laboratory value is identified, Investigators are strongly encouraged to report a diagnosis, or a sign or symptom rather than an isolated abnormal test value. An abnormal test finding should be documented as an AE if any of the following conditions are met:

- Is associated with a sign or symptom;
- Requires additional diagnostic testing (repeat tests are not considered additional testing);
- Requires a medical or surgical intervention;

- Leads to a change in study dosing outside of the protocol defined dosing or discontinuation from the study;
- Requires significant additional treatment;
- Does not meet any of the conditions above; however, the Investigator or Sponsor considers the result as clinically significant or meeting the definition of an AE.

This definition also includes the signs or symptoms resulting from:

- Drug overdose
- Drug withdrawal
- Drug misuse
- Drug interactions
- Extravasation
- Medication error
- Occupational exposure

An AE does not necessarily include the following:

- Medical or surgical procedures (eg, surgery, endoscopies, tooth extraction, transfusion); the condition that leads to the procedure is the AE (eg, laparoscopic cholecystectomy is the procedure or treatment for an SAE of necrotic gall bladder);
- Pre-existing diseases or conditions present or detected prior to the Screening evaluation that do not worsen;
- Situations where an untoward medical occurrence has not occurred (eg, hospitalization for elective surgery if planned prior to the start of the study, social and/or convenience admissions).

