### 12.5.6 Recording Adverse Events

All observed or volunteered AEs regardless of causal relationship must be reported as described in [Section 12.5.4](#).

For all AEs, the Investigator must obtain adequate information for the following:

1. determine the outcome of the AE;
2. determine if the event meets criteria for an SAE;
3. assess the severity of the AE;
4. determine the causality of the AE.

Adverse events must be documented in clear, unambiguous medical term. Study personnel are advised not to use abbreviations or acronyms.

For each AE, record only the diagnosis on the AE page of the CRF/eCRF. Do not report the characteristic signs and symptoms of the diagnosis as additional AEs.

If a diagnosis is not available, record each sign and symptom as an AE. When a diagnosis becomes available, study personnel are to update the source document and the AE page of the CRF/eCRF with relevant diagnosis only.

For medical or surgical procedures (eg, surgery, endoscopies, tooth extraction, transfusion), the condition/diagnosis that leads to the procedure should be recorded as the AE (eg, laparoscopic cholecystectomy is the procedure or treatment for an SAE of necrotic gall bladder).

All AEs that later increase in the frequency and/or severity (medical and scientific judgment should be exercised by the Investigator) will be considered new AEs and will be recorded on a new line in source and the CRF/eCRF.

Withdrawal due to an AE or SAE must be clearly differentiated from withdrawal due to other reasons.

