### 13.7.2 Secondary Efficacy Analyses

The secondary efficacy endpoints include:

- Change from baseline in urine and blood SSC levels
- Change from baseline in clinical findings from neurologic examination
- Change from baseline in age-appropriate motor and cognitive assessments (Bayley--III, GMFCS, WPPSI)
- Change from baseline in seizure frequency
- Change from baseline in neuroimaging
- Changes in growth parameters (body weight, body length, head circumference)
- Change from baseline in feeding patterns

Baseline is defined as the last available assessment prior to treatment with ORGN001 except for blood and urine biomarkers whereby baseline is defined as the average of all available assessments prior to treatment with ORGN001.

Observed urine and blood SSC levels as well as changes and percentage changes from baseline to the study time points will be summarized. Individual patient plots over time will be produced.

Shifts from baseline in clinical findings from neurologic examination and neuroimaging findings will be presented for the different time points. The frequency of seizures will be summarized.

Observed values and changes in GMFCS, WPPSI, and Bayley-III cognitive, language, and gross and fine motor scores will be summarized.

Growth parameters (weight [kg], length [cm], and head circumference [cm]) will be converted to age-adjusted z-scores and descriptive statistics will be presented for each parameter over time. In addition, the following individual patient's growth charts will be produced as specified in the statistical analysis plan (SAP) with a flag for start of ORGN001 infusion: Weight-for-age percentiles, length-for-age percentiles and head circumference-for-age-percentiles.

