4. DEFINITIONS

4.1. Efficacy

There is no pre-specified primary efficacy endpoint in this study. The secondary efficacy endpoints at all key study timepoints include:

- Change from baseline in urine and blood [REDACTED] levels
- Change from baseline in clinical findings from neurologic examination
- Change from baseline in age-appropriate motor and cognitive assessments (Bayley Scales of Infant Development-Third Edition [Bayley-III], The expanded and revised Gross Motor Function Classification System [GMFCS-E&R], Wechsler Preschool and Primary Scale of Intelligence [WPPSI])
- Change from baseline in seizure frequency
- Change from baseline in neuroimaging
- Changes in growth parameters (body weight, body length, head circumference)
- Change from baseline in feeding patterns

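### SAP 6.2.2.3 does not analyse the declared endpoint, change from baseline in seizure frequency; it compares shares of subjects with any seizure over an undefined pre-treatment window and 6-month periods

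*SAP*

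**What the plan says.** SAP 4.1 lists "Change from baseline in seizure frequency" among the secondary efficacy endpoints, as do Protocol 2.2.2 and 13.7.2. For the analysis, Protocol 13.7.2 states: "The frequency of seizures will be summarized".

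SAP 6.2.2.3, which has no redaction, plans four outputs:

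- "The number and frequency of subjects with seizures prior to treatment with ORGN001 and over each 6-month period on study will be summarized";
- the number of subjects whose medication changed because of seizures;
- a by-subject listing of seizure data and medication changes, with reasons;
- for events reported as adverse events: "Seizures collected as AEs will be summarized as AEs".

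On data collection, Protocol 9.5 and Table 3 footnote 21 provide for recall of the month before the first screening visit and then a daily diary for the whole study. Screening runs from Day -21 to Day -1. The general baseline rule in SAP 8.3 is the last available assessment before ORGN001.

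**The concern.** None of the four outputs is a seizure rate or a change in one. The SAP uses the same count-and-frequency-of-subjects phrasing for neuroimaging (6.2.2.4), feeding (6.2.2.5) and EEG (6.5.4.4), where it can only mean count and percentage. In 6.2.2.3, too, frequency therefore means the share of subjects. By contrast, SAP 6.2.2.2 and 6.2.2.6 ask for change from baseline in so many words. The readable text of SAP 3.1 declares no departure from the protocol analyses.

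The pre-treatment window is also undefined, and a last-assessment rule does not give a window for a count. If the dedicated data are used, 30 to 51 days are set against 6 months. If any earlier seizure counts, the bias could reverse, because Protocol 1.1 says the disease usually presents with seizures in the neonatal period. Neither reading compares like with like.

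This matters because Protocol 1.6 expects no change in clinical status after the switch from rcPMP and would take that as evidence of comparable efficacy. A rise produced by window length would obscure exactly that reading.

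The adverse event tables do not fill the gap. Worsening may appear there, since Protocol 12.5.1 counts "Exacerbations of a chronic or intermittent pre-existing condition including either an increase in frequency and/or intensity" as adverse events, and Protocol 12.5.6 has "All AEs that later increase in the frequency and/or severity" recorded as new events. But those tables give no rate, and they would not show improvement: "Pre-existing diseases or conditions present or detected prior to the Screening evaluation that do not worsen" need not be adverse events.

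**Working it through.** There is no figure in the plan to reproduce: the study has no hypothesis test, and its size (at least 4) is set by patient availability. The calculation below shows how the planned summary behaves.

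**Inputs from the documents.** One month of recall, taken as 30 days; up to 21 screening days, so 51 days at most; 6-month on-study periods; 4 patients. In months of 30.4375 days (the SAP 8.3 age divisor), the windows are t = 30/30.4375 = 0.986, t = 51/30.4375 = 1.676, and t = 6.

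**Assumed inputs.** The seizure rate r per month and its spread between patients, because the documents give neither.

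**Formulas for the chance of at least one seizure in a window.**

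- All patients share a constant rate r: P = 1 − exp(−r·t).
- Rates vary between patients as a gamma distribution with mean r and shape k (smaller k means more spread): P = 1 − (1 + r·t/k)^(−k).

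For example, with a shared rate of 0.3: 1 − exp(−0.3 × 0.986) = 0.256 before treatment, and 1 − exp(−0.3 × 6) = 0.835 on study.

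**No drug effect, r = 0.3 throughout**

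| Model | 30 days | 51 days | 6 months | False rise (points) |
|---|---|---|---|---|
| Shared rate | 0.256 | 0.395 | 0.835 | 44–58 |
| Gamma, k = 0.5 | 0.207 | 0.294 | 0.534 | 24–33 |
| Gamma, k = 0.1 | 0.129 | 0.164 | 0.255 | 9–13 |

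Multiplying by 4 patients, the expected number with seizures goes from 1.02–1.58 to 3.34 (shared), from 0.83–1.18 to 2.13 (k = 0.5), and from 0.51–0.66 to 1.02 (k = 0.1). The false rise is thus about 1.8–2.3, 1.0–1.3 and 0.4–0.5 children.

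**True halving, r = 0.3 before and 0.15 on study.** The 6-month share is 0.593 (shared), 0.402 (k = 0.5) and 0.206 (k = 0.1). Each exceeds its own 30-day and 51-day value in the table, so a real improvement reads as a rise.

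**True tenfold fall, r = 30 before and 3 on study**

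| Model | 30 days | 51 days | 6 months |
|---|---|---|---|
| Shared rate | 1.000 | 1.000 | 1.000 |
| Gamma, k = 0.5 | 0.871 | 0.901 | 0.836 |
| Gamma, k = 0.1 | 0.434 | 0.463 | 0.405 |

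The largest drop is 0.901 − 0.836, about 7 points.

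**Where the effect vanishes.** At r = 0 nothing moves. At a shared r = 4 the 30-day share is already 0.981 against 1.000 on study, a false rise of 2 points.

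**The case against.** The strongest reply is that the gap is smaller than it looks. SAP section 6 promises that all collected data will be presented, SAP 6.2 lists every endpoint, and SAP 8.3 defines change and percent change in general. With about 4 patients and a by-subject listing, a reader can follow each child's course. Successive on-study periods are equal in length, so only the pre-treatment comparison is affected. The SAP also follows part of the protocol: the synopsis efficacy variables and Table 3 footnote 21 speak of seizure incidence. The redacted SAP appendices cannot be checked for output specifications.

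Most of this stands as mitigation, but it does not close the gap. None of the general rules names a seizure rate or a window, and a listing does not replace the summary that Protocol 13.7.2 promises. The incidence wording shows that the inconsistency begins in the protocol; it does not remove it. The finding is confined to the readable text.

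The size can fairly be challenged. The rate of 0.3 per month is assumed and lies where unequal windows matter. The gamma model covers spread between patients, not clustering within one, and Protocol 9.5 anticipates flurries of seizures. If seizures came in clusters of 5 at the same mean, the cluster rate would be 0.3/5 = 0.06 per month. The share would then go from 1 − exp(−0.06 × 0.986) = 6%, or 1 − exp(−0.06 × 1.676) = 10%, to 1 − exp(−0.06 × 6) = 30%. That is a rise of 21 to 24 points where the unclustered shared rate gives 44 to 58. The direction survives; the size depends on the assumptions.

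**Conclusion.** The concern holds. As written, SAP 6.2.2.3 does not analyse the declared endpoint, and its before/after comparison rests on an undefined pre-treatment window. That conclusion comes from the text and needs no assumption about rates.

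The direction and size of the distortion are conditional. If the pre-treatment window is the 30 to 51 days of dedicated data and seizures are infrequent, the share rises with no change in rate. If seizures are frequent, the share hardly responds to a large improvement. If any earlier seizure counts, the bias could run the other way.

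The consequence is limited to the descriptive interpretation of one secondary endpoint in a small study without a hypothesis test. It should be fixed, because the fix is cheap and the planned display could mislead in either direction.

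**What to change.** In SAP 6.2.2.3:

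- Define the pre-treatment window and state that baseline is partly recall.
- For each patient, report seizures per fixed interval of observation (for example 28 observed days) in that window and in each on-study period, with change from baseline. Add percent change where baseline is non-zero, bearing in mind that it is unstable on a low baseline.
- If the diary records only whether a seizure occurred each day, report seizure days per the same interval.
- Compare any-seizure shares only across windows of equal length.
- Keep adverse event seizures in their own tables, as already planned, and do not add them to the diary count.

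Reconcile SAP 4.1.5, which describes a diary only for subjects who have seizures, with Protocol 9.5 and Table 3 footnote 21, which give one to every family. Observed diary days are the denominator for every patient.

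The incidence wording in the protocol synopsis should be aligned with the endpoint. If a protocol amendment is not otherwise planned, an SAP clarification would settle the analysis.

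The cost is SAP text and programming on data already collected. The difference between recall and diary at baseline will remain and should be stated as a limitation.

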6.2.2.4. Neuroimaging

Shifts from baseline [REDACTED] in findings from MRI or CT scan, if MRI/CT scan is contraindicated, will be presented for the different visits. A summary of the abnormal findings [REDACTED] [REDACTED] will be provided, as will the number and frequency of subjects with changes since previous neuroimaging.

6.2.2.5. Feeding Patterns

The number and frequency of subjects able to feed orally will be summarized by visit. For subjects that are not feeding orally, the feeding method will be summarized by visit. Results will also be included in by-subject listings.

6.2.2.6. Growth Parameters

Body weight, length, head circumference, and body mass index (BMI) will be analyzed by converting each parameter to age-adjusted z-scores and age percentiles and descriptive statistics will be presented for each parameter, as well as, for the change from baseline. The 5th, 25th, 50th, 75th, 90th, and 95th percentiles will be calculated.

Weight, length, head circumference, and BMI data including age-adjusted z-scores and percentile for each growth parameter-for-age will be presented in a by-subject data listing.

In addition, the following individual subject's growth charts will be produced with a flag for start of ORGN001 infusion and will include a symbol representing dose changed, if applicable: weight-for-age percentiles, length-for-age percentiles, head circumference-for-age percentiles, and BMI-for-age percentiles.

6.2.2.7. Pharmacodynamic Assessments

[REDACTED] Levels of biochemical markers that are measured in urine will be normalized to urine creatinine levels.

[REDACTED] The actual value, change, and percentage change from baseline in MoCD-associated urine and blood biomarker levels will be summarized by visit.

All [REDACTED] levels (plasma and urine) will be graphically displayed for each subject over time.

In addition, by subject plots will be graphically displayed, [REDACTED].

The percentage of change from baseline of each [REDACTED] (example: $([\text{Month } x - \text{Baseline}] / \text{Baseline} \times 100)$) will be plotted on the same figure.

6.2.3. Other Efficacy Analyses

Not applicable.

6.3. Pharmacokinetic Analyses

All PK analyses specified in the protocol will be performed [REDACTED].

6.4. Pharmacokinetic and Pharmacodynamic Analyses

The relationship between PK and plasma and urine SSC levels will be explored using graphic methods or PK/PD modeling.

6.5. Safety Analyses

All safety analyses will be conducted on the Safety Set. All safety data available at the time of database lock will be provided in subject listings. All AEs will be coded in the Medical Dictionary for Regulatory Activities (MedDRA) (version 22.0) and no formal hypothesis testing will be performed.

6.5.1. Study Duration, Treatment Compliance, and Exposure

Summary statistics (mean, SD, median, minimum, and maximum) will be produced for the following, using the FAS:

- Number of ORGN001 infusions
- Proportion of the number of infusions by expected number of infusions
- Number of make-up doses
- Number of missed doses
- Duration (days) of study participation from informed consent
- Total time (days/weeks/months) on ORGN001

By-subject listings will be produced for study duration, treatment compliance, and exposure, as well as, for study drug administration.

6.5.2. Dose Modification

The proportion of patients with dose modification (dose interruption, dose reduced, dose increased, dose stopped) will be listed and summarized using descriptive statistics. [REDACTED]

By-subject listings will be produced for dose modifications.

6.5.3. Adverse Events

Adverse events will be classified by system organ class (SOC) and preferred term (PT) using of MedDRA (version 22.0). The severity/relationship will be assessed.

The AEs will be determined as occurring prior to treatment with ORGN001 (pre-treatment), or as on or after first treatment (treatment-emergent), as described in [Section 8.3](#). Analyses of pre-treatment adverse events (PTAEs) and treatment-emergent adverse events (TEAEs) will be tabulated and presented separately. An incomplete date of AE onset will be compared to treatment start date, if unable to determine AE onset date is prior to treatment start, then AE will be considered a TEAE.

Subjects having multiple AEs within a category (e.g., overall, SOC, PT) will be counted once in that category. For severity/relationship tables, the subject's most severe/most related event within a category will be counted. Missing relationship to study drug will be considered treatment-related.

Percentages will be based on the total number of treated subjects in the Safety Set. Tables will be sorted by descending frequency of SOC and by descending frequency of PT within SOC. Listings will be provided for all TEAEs and PTAEs for the Safety Set. TEAEs with missing severity will not be included in the counts of patients within a SOC or PT; however, the event will be reported in listings.

AEs will include the displays described in the following sub-sections.

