## SYNOPSIS

Name of Sponsor/Company: Origin Biosciences, Inc. (Origin); previously; Alexion Pharmaceuticals, Inc. (Alexion)	
Name of Investigational Product: ORGN001 (formerly ALXN1101)	
Name of Active Ingredient: Cyclic pyranopterin monophosphate monohydrobromide dihydrate	
Title of Study: A Phase 2, Multicenter, Multinational, Open-Label, Dose-Escalation Study to Evaluate the Safety and Efficacy of ORGN001 (formerly ALXN1101) in Pediatric Patients with Molybdenum Cofactor Deficiency (MoCD) Type A Currently Treated with Recombinant Escherichia coli -derived Cyclic Pyranopterin Monophosphate (rcPMP)	
Study centers: This will be a multicenter, multinational study with approximately 5 investigational study centers.	
Principal Investigator: TBD	
Investigators: TBD	
Studied period: 6-Month Initial Treatment Period, followed by an Extension Period Estimated date first patient enrolled: February 2014 Estimated date last patient completed: The Extension Period is expected to last until ORGN001 is commercially available or development is stopped.	Phase of development: 2/3

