6.5.3.1. Overall Summary of Adverse Events

All PTAEs and TEAEs will be presented using summary statistics (n, %). The number of subjects with events (n, %) will be displayed.

Table 2: Treatment-Emergent Adverse Events

Relationship	Severity
Related AEs (possibly, probably, or definitely related, missing/unknown)	Mild AEs
Not related AEs (not related or unlikely related)	Moderate AEs
	Severe AEs

Additionally, the number and percentage of subjects who withdrew from the study due to an AE, discontinued treatment due to an AE, or who died on study will be presented. These statistics will be presented for all TEAEs and separately, for SAEs.

6.5.3.2. Adverse Events and Serious Adverse Events by System Organ Class and Preferred Term

The number of PTAEs and TEAEs and the number and percentage of subjects with events will be presented by SOC and PT.

6.5.3.3. Adverse Events and Serious Adverse Events by System Organ Class, Preferred Term, and Relationship

The number and percentage of subjects with TEAEs will be presented by SOC and PT as described above by relationship (related, not related). If a patient has more than 1 occurrence of an AE, the strongest relationship to study treatment will be used in the summary table. SAEs will be summarized similarly.

6.5.3.4. Adverse Events and Serious Adverse Events by System Organ Class, Preferred Term, and Severity

The number and percentage of subjects with TEAEs will be presented by SOC and PT as described above by severity (mild, moderate, severe). If a subject has more than one occurrence of an AE, the most severe occurrence will be used in the summary table. SAEs will be summarized similarly.

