For each subject, time on study from informed consent to last visit, study completion, termination or withdrawal (days) will be calculated as follows:

- For subjects who completed Month ■ = (date of Month ■ visit date – date of informed consent) + 1 day
- For subjects who withdrew prior to Month ■ = (date of study exit – date of informed consent) + 1 day

Additionally, for each subject, time on study from informed consent to last infusion will be similarly calculated.

Time on Study (months)

For each subject, time on study from informed consent to last visit, study completion, termination or withdrawal (months) will be calculated as follows:

- For subject who completed Month ■ = ((date of Month ■ visit date – date of informed consent) + 1 day)/30.4375, rounded to 1 decimal place
- For subjects who withdrew prior to Month ■ = ((date of study exit – date of informed consent) + 1 day)/30.4375, rounded to 1 decimal place

Additionally, for each subject, time on study from informed consent to last infusion will be similarly calculated.

Definition of Baseline Values

Baseline is defined as the last available assessment prior to treatment with ORGN001, except for growth parameters and blood and urine ■ where baseline is defined as the average of all available assessments on or prior to the date of first infusion with ORGN001.

Change from Baseline

Change from baseline will be calculated as follows:

Change of Baseline = Assessment Value – Baseline Assessment Value

Percent Change in Assessments from Baseline

Percent change in values from Baseline will be calculated as follows:

$$\% \text{ Change in Value} = \frac{(\text{Change in Value})}{\text{Baseline value}} \times 100$$

where Change in Value = (Assessment value – Baseline Assessment value), given that the baseline value is non-missing and non-zero and the subsequent value is non-missing.

Adverse Events

The analysis of AEs is described in detail in [Section 6.5.3](#). Subject percentages are based on the total number of treated subjects in the Safety Set.

Related AEs are defined as possible, probable, definitely related or unknown/missing. Unrelated AEs are defined as unlikely or not related.

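### The readable AE tables use one undivided treatment-emergent period and no patient-time, so they neither isolate the first 6 months nor show event frequency as treatment lengthens

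*SAP*

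**What the plan says.** **Denominator and counting.** SAP 6.5.3 states "Percentages will be based on the total number of treated subjects in the Safety Set", and SAP 8.3 repeats it: "Subject percentages are based on the total number of treated subjects in the Safety Set". The counting rule in 6.5.3 is "Subjects having multiple AEs within a category (e.g., overall, SOC, PT) will be counted once in that category".

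**Windows.** SAP 8.3 splits AEs at the first ORGN001 infusion into pre-treatment (PTAE) and treatment-emergent (TEAE), with no further division. SAP 6.5.3 adds "Analyses of pre-treatment adverse events (PTAEs) and treatment-emergent adverse events (TEAEs) will be tabulated and presented separately". Treatment is 180 days plus an extension, of which the Protocol Synopsis says "The Extension Period is expected to last until ORGN001 is commercially available or development is stopped".

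**Event counts and exposure.** SAP 6.5.3.2 plans "The number of PTAEs and TEAEs and the number and percentage of subjects with events will be presented by SOC and PT", and Protocol 13.8.1 also asks for both event and patient counts. SAP 6.5.1 summarizes "Total time (days/weeks/months) on ORGN001", but on the Full Analysis Set (FAS), while SAP 6.5 puts the safety analyses on the Safety Set.

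**Periods promised by the protocol.** Protocol 2.1.1 ties the primary objective to the first 6 months. Protocol 2.2 has every endpoint measured both over those 6 months and over all treatment. Long-term safety is a secondary objective (Protocol 2.1.2). SAP section 3 states the primary objective without the 6-month limit, and SAP 3.1 reports no changes from the protocol's analyses.

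**The concern.** A proportion of children with at least one event depends on how long they were watched. Here that time is unequal by design. Enrolment is sequential (Protocol 3.4), the extension has no fixed end, a child may leave once the drug is available in their region (Protocol 3.1), and those still on treatment are cut at the data cut-off (SAP 6.2.1.1).

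Two questions the protocol asks therefore have no dedicated AE table in the readable SAP: how safe the drug was in the first 6 months, and whether event frequency changes with longer treatment. SAP 6.2.2.3 does divide seizures into 6-month periods, so the omission for AEs is not explained by an inability to split the data. Without prespecified periods, any statement about either question would be assembled from listings after the data are known.

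**Working it through.** The documents give no AE rate, event count or precision target, and the minimum of 4 patients has no derivation, so there is no stated figure to reproduce. The check has two parts.

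**1. What the AE displays contain.** SAP 6.5.3 says its displays are those in its sub-sections. These are an overall summary, tables by SOC and PT, by relationship and by severity, and listings of SAEs, deaths and withdrawals. None that can be read uses patient-time, a rate, time to onset or a treatment period. The relationship and severity tables give subjects only, without event counts.

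**2. How far the percentage moves with time alone.** Inputs:

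- 21 days: the screening period (Protocol 3.1). This is nominal, since AEs are recorded from consent (Protocol 12.5), which may precede the Screening Visit (Protocol 4.1).
- 180 days: the initial treatment period (Protocol 3.1).
- 4.5 years: an assumption. First enrolment was estimated for February 2014 (Protocol Synopsis) and the drug dictionary is dated September 2018 (SAP 6.1.5), which suggests roughly this for an early enrollee.
- Rate: assumed constant at 0.1 to 2 events per patient-year, the same in every window.

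Expected share with at least one event = 1 − exp(−rate × years), with 21/365.25 = 0.057 and 180/365.25 = 0.493 years.

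| Assumed rate per patient-year | 21 days | 180 days | 4.5 years |
|---|---|---|---|
| 0.1 | 0.6% | 4.8% | 36.2% |
| 0.5 | 2.8% | 21.8% | 89.5% |
| 2 | 10.9% | 62.7% | 100.0% (rounded) |

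Example: 1 − exp(−0.5 × 0.493) = 0.218. The 180-day window alone is 180/21 = 8.6 times the nominal screening window.

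**With patient-time as denominator**, 4 children at 0.5 per patient-year give:

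- 21 days: 4 × 0.057 = 0.23 patient-years, 0.11 expected events
- 180 days: 4 × 0.493 = 1.97 patient-years, 0.99 expected events
- 4.5 years: 4 × 4.5 = 18 patient-years, 9 expected events

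Each ratio is 0.5, so the figure no longer depends on the window.

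**Precision stays poor.** With zero events the exact two-sided 95% upper limit is −ln(0.025)/patient-years = 3.69/patient-years. That is 16.0 per patient-year for 21 days, 1.87 for 180 days and 0.20 for 4.5 years. Nine events in 18 patient-years give 0.23 to 0.95. These limits treat events as independent.

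**The case against.** **The data for a rate are already reported.** Event counts by SOC and PT, time on ORGN001, by-subject exposure listings, and AE, SAE and death listings are all planned. An overall rate is one division away, and with about 4 children the dated listings carry much of the evidence. Laboratory tests, vital signs, physical examination and EEG are summarized by visit (SAP 6.5.4). This stands. A reader might infer that the plan cannot answer the long-term safety objective, and the documents do not support that. What remains is that rates by period are not prespecified and no readable AE table shows the 6-month period.

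**No comparison with rcPMP is planned.** A reader might infer that the tables will make ORGN001 look worse than rcPMP. However, the design is noncomparative (Protocol 1.6), nothing is tested, and PTAEs and TEAEs are tabulated separately. The risk is a misreading of two percentages on the same denominator, which a footnote can prevent.

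**Saturation depends on the rate.** At 0.1 per patient-year only 36.2% would have an event in 4.5 years, so rarer SAEs and preferred terms need not approach 100%. This is correct, but the percentage still rises with follow-up at every rate.

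**Redaction.** Extension details, the visit-window table and later appendices are blacked out. A period split could be there, so the point covers the readable text only.

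**Rates bring their own problems.** Repeated events within a child are correlated, and Protocol 12.5.6 records each worsening of an AE as a new AE. Simple Poisson intervals would be too narrow. This is accepted and shapes the change proposed.

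**Conclusion.** The point holds within limits. In the readable SAP, AE incidence is a crude percentage over one undivided period of unequal and open-ended length, without the 6-month split that the protocol's objective and endpoints call for. At a constant rate the percentage rises severalfold from observation time alone: at 0.5 per patient-year, from 21.8% in 180 days to 89.5% in 4.5 years. The direction does not depend on the rate chosen. The size does, and it rests on an assumed constant rate and an assumed 4.5 years, neither of which is a figure in the documents.

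This is a gap in prespecification and presentation that should be closed. It does not invalidate the planned safety reporting.

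**What to change.** In SAP 6.5.3:

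1. Present TEAEs and SAEs for the first 6 months and for the entire treatment period, as Protocol 2.2 requires, and for stated later intervals of the extension.
2. For each, give subjects at risk, patient-years, number of events and events per patient-year.
3. Compute patient-years on the Safety Set. Section 6.5.1 now uses the FAS. By SAP section 5 the two differ only if a treated child is not MoCD Type A, but numerator and denominator must match. Section 6.5.1 lists no time by period, so add that derivation, with the data cut-off as the end for children still on treatment.
4. Label any exact Poisson interval as descriptive, and note that repeated events within a child make it too narrow. An interval based on subjects with a first event is an alternative.
5. Footnote the tables: crude PTAE and TEAE percentages cover windows of different length and are not to be compared.

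Cost: one or two added tables and a short derivation, with no new data collection. The rates will be very imprecise at about 4 patients, because patient-time improves comparability, not precision.
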